### **Safety Training for investigators:**

Infection control team of Kowloon Hospital provided safety training to all participants of research team. Infection control nurse described the safety measures according to hospital safety guidelines. After full day training, participants were assessed by written question about using of person protective equipment including mask, gloves, gowns, and caps. All successful participants were allowed to become a part of investigating team. Ward managers in pathology and rehabilitation wards also explained about emergency exits and dealing with emergency in case of any accident during working hours. Finally, all participants were provided with staff access cards with validity till completion of study (June 30, 2018).

### **Pre-sampling arrangement:**

#### 1. Preparation of neutralizing solution:

- Neutralizing solution: 1-liter preparation, (Polysorbate/Tween 80, 30 g/L; Saponin, 30 g/L; and lecithin, 3 g/L; pH 7.0).
- As normal preparation, pH was 5-6, so we used NaOH as a base to bring pH at 7.
- According to sampling plan the required 20 liters neutralizing solution was prepared on weekly basis by keeping it sterilized to prevent contamination that might gave false positive results.

#### 2. Preparation of spreading beads:

- For 100 $\mu$ l solution spread on agar medial on agar plates, we poured 5-10 beads on each plate and shake gently until all liquid media spread and absorbed.
- All the beads were pre autoclaved and sterilized to prevent contamination.

#### 3. Pouring of neutralizer into sponge containing zip bags:

- 10ml of neutralizing solution was poured into sterilized empty zip plastic bags.
- We used a new 10ml pipette glass tube and electric pipette to pour neutralizer on

operation bench in KH core lab, before sampling.

c. The team dealing with neutralizer pouring was operating carefully to measure the appropriate amount, prevent spoilage and maintain hygiene and safety.

d. Zipped bags were opened minimally, to reduce the chances of contamination.

4. Labelling:

a. All the bags were labelled before sampling

b. Labelled the bags with bed number, coding, sampling area

5. Transportation Containers:

a. Sampling material containers were have following items to bring in rehabilitation ward (1 set for male and similar another set for female cubicle) for 1-time sampling:

- Polywipe sponges 110, (required 96, extra 14 in case of contamination/ fall in floor during sampling)
- Plastic gloves (blue colored), already given in polywipe sponge box
- Plastic holding clips, to identify measured area
- Measuring tapes, to measure 50x50cm^2 area as a sampling area
- Neutralizing solution in zipped labelled bags 110, (required 96, extra 14 in case of contamination/ fall in floor/ leakage)
- Autoclave medium size bag to put used gloves used sponge and wrappers of sponge

## **Sampling Arrangements and methods:**

1. Sampling Cubicles (Location): one male cubicle (3rd cubicle) and one female cubicle were allocated for this study after pilot study results. These were located on 3rd floor or rehabilitation building (ward 3B).

2. Sampling time: Every visit, sampling was started at 8:30 am and finished till 12:00 pm.

3. Following the Rules: Sampling team had to follow the rules of Kowloon Hospital in rehab wards. The team had to sample curtains smoothly and quietly to minimize disturbance to working staff as well as patients in beds. The team was not allowed to encroach patient treatment or investigations/ file to keep the confidentiality.

4. Gowning for safety: All the members were gowned properly by wearing personal protective equipment (disposable gown, gloves, mask and head cover). For gowning, individual followed the step mentioned in safety training, as all sampling taking persons had gone through safety training by infection control team of Kowloon Hospital.

5. Sample taking notification and Consent: Team was notifying ward manager/ ward in-charge about sampling plan and take verbal permission to proceed.

6. Sampling Teams: In the female cubicle, two female team members took samples. One

member was take a sample of swabbing the area; other was helping to provide gloves, sponge, identification of appropriate area, calibrate the size and provide support by holding the frame of 50x50cm^2. The same sampling protocol was adopted in a male cubicle where male team members were taking the samples.

7. Safety precaution:

Following safety measures were accomplished before and during sampling:

- a. Before sampling, clean the hands having gloves with available disinfectant.
- b. Put plastic disposable gloves and take out sponge from its plastic packing.
- c. Again disinfect plastic gloves and let it dry for few second.
- d. Hold the sponge firmly from one side and keep sampling designed 50x50cm^2 area.
- e. Don't touch any other, other area holding the sponge, and prevent felling down on contaminated floor
- f. In case, sponge was touch with other surface or fell on floor, please discard that sponge and resample the same area with a new sponge

8. Sample preservation:

- a. After proper sampling, we put the sponge in zipped plastic bag containing 10 ml neutralizing solution quickly to reduce chance of contamination
- b. 2nd team member opened the zipped bag for sampling member for convenient proceeding
- c. The 2nd team member zipped up the sampling bag aseptically, confirmed the correct labeling, and kept in an aseptic container.
- d. 2nd team member also mixed the neutralizer gently with a sampled sponge
- e. Sponge sample in neutralizing solution bag were kept in a safe container until all the sampling was not completed.

9. Degowning and Transportation:

- a. After completion of all samples from patient privacy curtains, the team were degowning according to the protocol by removing PPE.
- b. Transportation boxes were brought back to pathology core lab of KH from rehabilitation ward immediately after completion of sampling.
- c. Transportation containers were brought back by holding with one hand gloved another hand without gloves according to infection prevention policy

[figure not shown]
[figure not shown]
[figure not shown]

Fig 4. Illustration of sampling method on curtains in Kowloon Hospital, preservation and inoculation on TSA and Chromagar plates

## Post Sampling Procedures:

1. Arrangements of Agar Media Plates: Queen Elizabeth Hospital's (QEH) Media preparation unit prepared TSA and Chromagar MRSA agar plates according to needs of this research.
    - a. Principal investigator was notifying [name] (coordinator for media preparation on QEH) two weeks ago about the preparation of required media plates.
    - b. All the prepared media was preserved at 3-4°C in QEH. Media plates boxes were labelled as HKUST-TSA and HKUST-MRSA plates in different batches.
    - c. Prepared boxed were transferred to Kowloon Hospital's cold room for long term use as well as prevention from contamination.
    - d. For the media preparation, sampling team coordinated by emails or meet them in person if there was any change in requirement.
  2. Agar plates Standardization: As the agar plates were kept at lower temperature (3-4°C), agar plates should normalize to normal room temperature as recommended. We kept out the agar plates on the desk before going for sampling, and in the meanwhile, plates were ready to use after 3-4 hrs.
  3. Unboxing and labelling of agar plates: All the prepared plates were packed in boxes, so before using the plates, team was unboxing, calculating and separating two type of media plates. Each plate was labelled as
    - a. Code, i.e., 1040
    - b. Sampling area number (1-8)
    - c. Plate number (first or duplicate)
    - d. Location (Male/ Female)  
i.e. (M-1040-4-2)Male-code 1040- Area 4- sample 2
- 
4. Sample inoculation area: Samples were inoculated on the desks in Kowloon hospital pathology core lab. All the team members were participating in this procedure following safety measure, wearing PPE.
  5. Mixing of Sponges containing neutralizer bag: Before taking 100µl of a neutralizing solution, it was compulsory to mix sponge very well so that all suspected microbes would come out from the sponge into the solution. Mixing was gentle, continuous and for the period of a minimum 1 minute.
  6. Dilution in PBS: 100µl of neutralizing solution was diluted in 900µl of PBS, mixed well and then 100µl was put on agar plated to inoculate. This was performed for TSA plates because bacterial load was high and plates were unable to read.
  7. Inoculation Procedure:
    - a. 100µl of well mixed neutralizing solution was dropped by using 100 -200 µl pipette with sterilized pipette tube on Chromagar MRSA plates and spread homogenously

- by sterilized beads by gentle shaking
- b. 100µl of solution from PBS mixed solution was dropped by using 100 -200 µl pipette with sterilized pipette tube on TSA plates and spread homogenously by sterilized beads by gentle shaking
  - c. All the plated were shaken well in clock wise circular motion for 1-2 minutes for homogenous spread
  - d. When there was not a visible solution on agar plates, opened the agar plates and took out beads in autoclave bag respectively.
  - e. All inoculated agar plates were finally transferred to an incubator and kept for 48hours at 37°C.
  - f. Inoculated plates were transferred in a specified labelled container to prevent any infection spread or spoilage

[figure not shown]

Fig 5. Illustration of incubation, enumeration and decontamination with autoclave in pathology ward of Kowloon Hospital

8. Cleaning inoculation area: All the desks were cleaned with bleach (NaClO) or other available disinfectant, recommended by hospital infection control authority using cotton wipes. All touched surface, including inoculated transfer container, was cleaned with recommended disinfectant.
9. Results:
  - a. At 48hrs, all the plates were counted to calculate CFU/m^2.
  - b. TSA (Tryptic Soya Agar) was used to count total bacteria. The colonies were pale to yellow in the circular pattern. The average number of colonies was 50-250 on TSA plates as PBS diluted factor.
  - c. Chromagar MRSA was used a selective media to check MRSA. MRSA appeared as Purple to Pink rounded colonies. In case of yellow or blue colonies growth on media, we did not count those unknown gram positive bacteria.
  - d. Counted plated were wrapped with plastic tape and put in autoclave bags to autoclave clinical waste. KH staff helped to autoclave used plates for safety measures.

- e. After discarding counted plates safely, the counting area, material touched or exposed was cleaned using standard disinfection.
- f. Results were saved in an official register for keeping the data in privacy
- g. All the data was uploaded to excel sheet and analyzed for a bacterial reduction on comparative ends of control and treatment curtains.
- h. Weekly, data was assessed and shared with [name] [name] along with a central continuous excel sheet with raw data.
- i. HKUST team also shared the results with KH and QEH research team on a monthly basis as a summarized report and brief power point briefing session in the conference room of KH after coordination.

### **Data Analysis:**

The duplicate system in total bacteria count helped to monitor the validity of the data point. Logical elimination of plate count was determined while comparing the bacteria morphology of the first plate with the second plate. If the bacteria morphology was not consistent, the plate with more bacteria was eliminated, and the plate with a lower value was taken due to the chance of contamination on a non-selective agar plate.

The Colony Forming Unit (CFU) obtained on the duplicated plates was averaged, and the CFU per unit area was calculated. CFU per unit area was allowing the comparison of microbiological contamination of the sampled surface. With the dilution factor of the samples, the Total bacteria count (TBC) was determined. The microbiological contamination level of an item was represented by the CFU/unit area of the item.

CFU on Müller-Hinton Agar represents the total aerobic bacteria count. By dividing the CFU with the area sampled, CFU/m^2 was obtained. Data points that did not contain any CFU count were assumed to have 0.5 CFU. The assumption was made based on the minimum detection value that can be obtained.

All analysis was carried out using Statistical Package for the Social Sciences for Windows, version 25.0 (SPSS, Inc., Chicago, IL, USA) to analyze the effectiveness of the coating in reducing the contamination level of the surface. The total bacteria count on the patient partition curtains was compared to the control and treatment group using Mann-Whitney test and T-test. Chi-square test and Fisher's exact test were also used to compare categorical variables such as the percentage of MRSA. Parametric test was carried out to evaluate the cleanliness baseline in each of the wards before and after treatment. ANOVA analysis allowed the comparison of different periods of study and the differences among wards. Median time to first contamination (days) of MDRO for each curtain type was compared using the Wilcoxon rank-sum test. The significance of the statistical test was defined to have a P value <0.05.

Healthcare workers from the participating wards were assessed for their acceptance of the multilevel antimicrobial disinfectant coating by way of a questionnaire. Additional reformulation may be necessary to increase the acceptability of the coating technology to the healthcare workers.

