### Sampling Duration, Time Frame, and work plan:

Background /Pilot Study	Survey	Observation Period (1 st Data Set/Phase 1 )	Washo ut	Survey	Observation Period (2 nd Data Set/ Phase 2)	Wash out	Survey	Observation Period (3 rd Data Set/ Phase 3)
8 weeks	4 weeks	4 weeks	3 week	2 Week	4 weeks	3 week	2 week	4 weeks
04 Sep -30 Oct (2017)	31 Oct – 28 Nov (2017)	01 Dec - 30 Dec (2017)	1st Jan - 05 Feb (2018)		06 Feb – 08 Mar (2018)	26 Mar – 30 Apr (2018)		22 May – 20 Jun (2018)
		8 curtains from Male  12 curtains from Female Cubicle  50% coated curtain, 50% standard curtain			12 Curtains from Male Cubicles  12 Curtains from Female Cubicle  50% coated curtain, 50% standard curtain			16 Curtains from Male Cubicles  16 Curtains from Female Cubicle  50% coated curtain, 50% standard curtain
		No of samples: 480			No of samples: 576			No of samples: 768

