half of the curtains as control in the same setting in a cubicle. As the study was double blind, so coding was done to identify the treatment as control curtains.

[5] Sample were taken from eight highly touched areas of 50x50 cm^2 on weekly bases for three consecutive weeks on 7th day of first installation. On each period/phase 480, 576 and 786 samples were collected accordingly using the developed sample protocol. In total, the investigators collected 1824 samples from 76 patient privacy curtains in which 912 (50%) were control curtain and 912 (50%) are antimicrobial coated curtains.

[6] Healthcare workers from the participating wards were assessed for their acceptance of the multilevel antimicrobial disinfectant coating by way of a questionnaire. Additional reformulation may be necessary to increase the acceptability of the coating technology to the healthcare workers.

[7] For the bacteria count, duplicate plates of TSA (total bacteria count) and Chromagar MRSA (selective agar for MRSA detection) were used for enumeration. CFU/m^2 is calculated after 48 hours' incubation at 37C. Data was analyzed using SPSS V.21 to assess the effectiveness of the coating in reducing the contamination level of the surface. The total bacteria count on the patient privacy curtains was compared between the control and treatment group using Mann-Whitney test and T-test. ANOVA analysis allowed the comparison of different periods of study of phase wise as well as week wise. The significance of the statistical test is defined to have a P value <0.05.

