## 2. Curtain installation:

1. Every 3rd week, our team changed the curtains from 2 cubicles (1 male and one female) according to curtain changing policy of hospital.
2. At the start of every phase of study, following the standard protocol; after taking official consent from ward manager we changed the curtains at once from both cubicles.
3. There were two types of curtains clippings, with metal ring and cloth strips so that curtains were changed according to the type of clips/ring.
4. As there was the capacity of 12 curtains in one cubicle, so six curtains were coated and six uncoated. The sequence was alternative as one coated next uncoated and so on. After installation, we informed ward manager about completion of curtain hanging in the designated ward and took first sample at day 7 because we gave sufficient time to curtains to be contaminate in hospital environment.
5. There was a backup pair of the curtain in case of need to change curtain due to spoilage, vomitus, blood or MDRO diagnosed the patient. Staff was informed to notify our team about the date and reason of curtain changing.

[figure not shown]

Fig 2. Illustration of curtains installation in cubicles as one control other treatment showing matched paired randomization

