### Basic information of previous field study in orthopedic ward

#### Assumptions:

1. The sample taken may have a higher standard deviation than the previous study. SD assumed to be 1log.
2. 0.21 log reduction on the total bacteria count on the bed partition curtains was assumed. This was based on the difference of the control and the treatment group in the previous study.

t tests - Means: Difference between two independent means (two groups)

Analysis: A priori: Compute required sample size

Input: Tail(s) = One  
 Effect size d = 0.2000000  
 α err prob = 0.05

	Power (1- $\beta$ err prob)	=	0.95
	Allocation ratio N2/N1	=	1
Output:	Noncentrality parameter $\delta$	=	3.2924155
	Critical t	=	1.6462631
	Df	=	1082
	Sample size group 1	=	542
	Sample size group 2	=	542
	Total sample size	=	1084
	Actual power	=	0.9500669

Hence a minimum of 1084 specimens were adequate for our study. To best fit the wards size and sampling schedule, we reckon a sample size of 1800 was best suited for our study.

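### The coated-versus-control tests ignore the phase and cubicle blocks within which the arms were balanced; this costs power once the curtain is the unit of analysis, and the blocks should enter a curtain-level model.

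*Combined protocol and SAP*

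**What the plan says.** **Arm comparison.** Data Analysis states: "The total bacteria count on the patient partition curtains was compared to the control and treatment group using Mann-Whitney test and T-test". Paragraph [7] of the Detailed Description names the same two tests. Neither place mentions a phase, cubicle or pair term.

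**Phase and ward.** These appear only in an ANOVA. In the Detailed Description, "ANOVA analysis allowed the comparison of different periods of study of phase wise as well as week wise"; in Data Analysis, "ANOVA analysis allowed the comparison of different periods of study and the differences among wards". The ANOVA's factors are not listed, and it is not described as adjusting the arm comparison. The threshold is given as "The significance of the statistical test was defined to have a P value <0.05".

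**Layout.** The work-plan table gives "50% coated curtain, 50% standard curtain" for each phase, with 8 male and 12 female curtains in phase 1, 12 and 12 in phase 2, and 16 and 16 in phase 3. Curtain installation, item 4, adds: "As there was the capacity of 12 curtains in one cubicle, so six curtains were coated and six uncoated", hung alternately. The caption of Fig 2 describes the layout as matched pairs.

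**Sample size.** The G-Power calculation is for two independent groups, one-sided, "α err prob = 0.05", d = 0.20, with a single SD of 1 log. The Detailed Description totals the data as 912 samples per arm from 76 curtains.

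**The concern.** A design that balances arms within blocks removes block differences from the arm contrast. The analysis has to reflect this, or the standard error still carries variance that the design has already removed. The phases run from December to June, and the plan itself sets out to test whether periods differ, so a phase effect is plausible. A two-sample test that ignores phase and cubicle leaves that variance in its error term.

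At stake is the power of primary outcome 1, and also how the analysis is repaired. Each curtain contributes 24 swabs (8 areas × 3 weeks), so a sound analysis will move to the curtain as the unit. The comparison then rests on 38 curtains per arm, and a correction for clustering that left the blocks out would give away much of the efficiency the layout provides.

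**Working it through.** **1. The plan's own figure.** Two-sample t-test, d = 0.20, one-sided 0.05, power 0.95: the noncentral t gives 542 per arm (1084 in total), δ = 3.2924, critical t = 1.6463 and power 0.95007, all as printed. At 912 independent swabs per arm, power is 99.6% one-sided and 99.0% two-sided.

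**2. Inputs for the check.**
- From the documents: 20, 24 and 32 curtains by phase (76 in all), 24 swabs per curtain, SD 1 log, effect 0.20 log, one-sided 5%.
- Assumed, because the documents give neither: the ICC of swabs within a curtain (0.05, also 0.10), and phase shifts, with phase 1 lower and phase 3 higher than phase 2 by s.

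**3. Curtain means.**
- Variance of a curtain mean within a block: ICC + (1 − ICC)/24 = 0.05 + 0.95/24 = 0.0896.
- True standard error of the arm difference, with blocks balanced: √(0.0896 × 2/38) = 0.0687.
- Between-phase variance: B = s²(20 + 32)/76 − [s(32 − 20)/76]². For s = 0.2, B = 0.0274 − 0.0010 = 0.0264. For s = 0.3, B = 0.0616 − 0.0022 = 0.0593.
- Standard error used by the unstratified test: √((0.0896 + B) × 2/38). This is 0.0781 at s = 0.2 and 0.0885 at s = 0.3, against a true 0.0687.
- At s = 0.3 the unstratified test needs a difference of 1.666 × 0.0885 = 0.1475. Power is Φ((0.20 − 0.1475)/0.0687) ≈ 78%, and true one-sided error is Φ(−0.1475/0.0687) ≈ 1.6%.

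Simulation with 20,000 trials per setting (two-sample t-test against a linear model with arm plus six strata) agrees:

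| ICC | s (log) | Unstratified power | Stratified power | Unstratified one-sided error |
|---|---|---|---|---|
| 0.05 | 0 | 89% | 89% | about 5% |
| 0.05 | 0.2 | 84% | 89% | 3.0% |
| 0.05 | 0.3 | 77% | 89% | 1.8% |
| 0.05 | 0.5 | 54% | 89% | 0.2% |
| 0.10 | 0.3 | 64% | 75% | – |

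**4. Swabs, 912 versus 912.**
- If swabs are taken as independent, as the sample-size calculation does, let r be the share of variance lying between strata (assumed). With SD 1 as the within-stratum SD, two-sided power falls from 99.0% stratified to 98.6%, 98.1% and 97.3% pooled at r = 0.1, 0.2 and 0.3, a loss of at most 1.7 points. With SD 1 as the total SD, the loss is 0.2 to 0.3 points.
- With ICC 0.05 and s = 0.3, the swab-level test uses √((1 + 0.0593) × 2/912) = 0.0482, while the true standard error is still 0.0687. Its critical difference is 1.646 × 0.0482 = 0.0793. One-sided error is Φ(−0.0793/0.0687) ≈ 12%, and power is Φ((0.20 − 0.0793)/0.0687) ≈ 96%. At s = 0.2 the error is about 13%.
- The ratio of true to assumed variance is (1 − r)(1 + 23 × ICC). It exceeds 1 once the ICC passes 0.005, 0.011 and 0.019 for r = 0.1, 0.2 and 0.3. Above those values clustering outweighs the blocking.

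**5. Strata added to the swab-level test alone.** At r = 0.2 and ICC 0.05, simulated two-sided error rises from 0.143 to 0.192. Taking block variance out of an error term that is already too small makes the error rate worse.

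**The case against.** The strongest objection is that the test the plan appears to use works on swabs, and there the blocks hardly matter. A reader might infer from the unstratified error term that the planned p-value is conservative, the interval too wide and a real effect likely to be missed. The documents do not support that for 912 versus 912 swabs. On the plan's own inputs power is about 99%, and once swabs within a curtain are even slightly correlated the test is anti-conservative. This part of the objection stands in full.

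Two further points stand in part.

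- **Phase variance may be counted twice.** The SD of 1 log was chosen to exceed the 0.53–0.54 seen in a previous study that ran for a year, so it may already include variation over time. Holding the total SD at 1 does not close the gap, however. With r = 0.1 and ICC 0.05, curtain-level power (two-sided 5%) is about 86% stratified and 54% unstratified. What remains is that the documents give no between-phase or between-cubicle variance, so the size of the loss is conditional. The 54% in the simulation table needs a 1.0 log swing between phases 1 and 3.
- **Pooling is inferred.** No sentence says the phases were combined without stratification. The inference is fair: the tests are named without strata, the outcome's time frame is the full 12 weeks, and the totals are given as 912 per arm. It is still an inference. The six/six split also describes a 12-curtain cubicle, whereas phase 3 lists 16 curtains per sex, so balance within the individual cubicles of that phase is not documented.

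**Conclusion.** The point holds as a loss of efficiency in a curtain-level analysis. The named tests leave out the blocks. The balance protects the estimate from bias but does not, in an unstratified test, reduce the standard error. With 38 curtains per arm and an ICC of 0.05, the cost is about 5 points of power at phase shifts of ±0.2 log and about 12 points at ±0.3 log; at ICC 0.10 and ±0.3 log it is about 11 points. If phases do not differ, stratifying costs practically nothing. These sizes rest on assumed ICCs and shifts and should be re-estimated from the data.

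It does not hold as a statement that the swab-level test is conservative or underpowered. There the block effect on power is under 2 points for r up to 0.3, and the dominant fault is treating 24 swabs per curtain as independent, with one-sided error of about 12–13% at ICC 0.05. The two faults need to be corrected together.

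**What to change.** For the primary coated-versus-control comparison, analyse log10 counts with the curtain as the unit and the blocks in the model:

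- Fit a linear model to curtain means with arm plus phase-by-cubicle strata. Equivalently, fit a mixed model to swabs with a curtain random effect and the same strata.
- Replace the Mann-Whitney test with a van Elteren test on curtain means over those strata.
- Report the arm difference with its 95% CI from the model.
- Do not add strata to the swab-level test while swabs are still treated as independent.
- Define the strata by the cubicles actually used. Phase 3 lists 16 curtains per sex against a capacity of 12 per cubicle, so the documents should state which cubicles were used and how the arms were split within them.

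The cost is a change of wording and a re-run. Plates carry the curtain code and the male or female location, sample bags carry the bed number, and phase should follow from the sampling date. Six strata use five degrees of freedom, and each further cubicle uses one more. No new data are needed.

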## **Detailed Description:**

[1] A multi-level antimicrobial coating was produced in the HKUST laboratory using the newly developed staged flow micromixing to prepare contact-killing and anti-adhesion coating made of US-FDA approved polymeric materials. The process was optimized to scale-up the production to 5 liters per hour. 300 liters of the multi-level antimicrobial coating was prepared for the study for a total of 24 weeks as three liters of the coating was needed for one patient privacy curtain.

[2] The study was conducted in the rehabilitation ward of the Kowloon Hospital including both male and female cubicles. It was carried out in three stages with each stage consisting of survey and a four weeks' observation period, separated by three weeks' washout period. In the rehabilitation ward of Kowloon Hospital, a set of male and female cubicle was recruited for the study after getting maximum number of bacterial contamination on patient privacy curtains in pilot study of 8 weeks. Each cubicle had 12 curtains besides admitted patients where all the samples are collected.

[3] Environmental sampling was carried out using sponge swab on the surfaces of the patient privacy curtains. The total bacteria count and quantitative isolation of MRSA was done using established protocols. The total bacteria count provides a quantitative measure of surface cleanliness, while the MRSA count was indicative of the risk of contact transmission from contaminated surfaces. 2-4 weeks survey provided control data on the cleanliness of patients privacy curtains in terms of total bacteria and MRSA counts.

During the study period, the Kowloon Hospital/Queen Elizabeth Hospital infection control team monitored MDROs regularly as part of their routine operation. The procedure and schedule was followed strictly the infection control protocol. All infection control measures implemented after isolation of MDROs were followed according to the hospital's usual practice as advised by the infection control team. In the study, the identification of the organisms in patients more than 48 hours after admission without prior isolation of the organisms in clinical or screening specimens was defined as nosocomial.

[4] The investigators demonstrated a cross-over intervention study. In the first stage of study, half of the patient privacy curtains were considered as treatment (antimicrobial coated) and the other

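### The before-after test of ward cleanliness has no concurrent control: it takes in any time trend in full and, if pooled by ward, shows only about half of a true coating effect

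*Combined protocol and SAP*

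**What the plan says.** The statistical paragraph of Data Analysis states its purpose as judging how well the coating lowers surface contamination. It lists Mann-Whitney and t-tests of coated against control curtains, and chi-square and Fisher tests for MRSA. It then states: "Parametric test was carried out to evaluate the cleanliness baseline in each of the wards before and after treatment". An ANOVA across periods and wards and a Wilcoxon test of time to first contamination follow. One threshold, P<0.05, covers them all. The before-after sentence names no curtain type, no comparator, no model and no data set for before.

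Other sections supply the context:

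- Detailed Description [2] sets out "three stages with each stage consisting of survey and a four weeks' observation period, separated by three weeks' washout period". It says the male and female cubicles were "recruited for the study after getting maximum number of bacterial contamination on patient privacy curtains in pilot study of 8 weeks".
- Detailed Description [3] says the "2-4 weeks survey provided control data on the cleanliness of patients privacy curtains in terms of total bacteria and MRSA counts".
- Curtain installation puts 12 curtains in a cubicle, six coated alternating with six uncoated, and says all were changed together at the start of each phase.
- Primary Outcome Measure 1 compares mean counts on control and treatment curtains.

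**The concern.** A before-after comparison attributes to the coating everything that changed between the two periods. Here that includes the calendar and possibly how long the curtains had been hanging, since the documents do not give the age of the curtains sampled in the surveys. Because the test is per ward rather than per curtain type, it may also average over curtains that were never coated. Nothing labels it descriptive. A significant fall could therefore be read as reduced contamination due to the coating when it is a time trend. Equally, a real effect could be masked by dilution or by an opposite trend. The choice of cubicles on their pilot results adds a further risk, but only if pilot data enter the before values.

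**Working it through.** **1. The effect the plan expects.** The G-power output uses d = 0.20, one-sided alpha 0.05 and power 0.95. Then n per group = 2(1.645 + 1.645)²/0.20² = 541.2, rounded up to 542, or 1,084 in total. This reproduces the plan. With the assumed SD of 1 log, d = 0.20 is 0.20 log. The previous study's means give 4.32627 − 4.13126 = 0.195 log, and the listed assumption is 0.21 log.

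**2. Dates in the work plan.**

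| Period | Dates |
|---|---|
| Pilot | 4 Sep to 30 Oct 2017 |
| Survey 1 | 31 Oct to 28 Nov 2017 |
| Phase 1 | 1 to 30 Dec 2017 |
| Washout and survey 2 | 1 Jan to 5 Feb 2018 |
| Phase 2 | 6 Feb to 8 Mar 2018 |
| Washout and survey 3 | 26 Mar to 30 Apr 2018 |
| Phase 3 | 22 May to 20 Jun 2018 |

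Every candidate for before precedes its phase. As the table reads, the third washout and survey block ends 21 clear days before phase 3 starts.

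**3. Dilution and drift.** Let δ be the true log reduction on coated curtains and s the change over time common to all curtains. With half the curtains coated:

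- pooled before-after change = s − δ/2
- change on coated curtains alone = s − δ
- change on control curtains = s
- coated minus control = −δ

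With s = 0, the pooled change is 0.195/2 = 0.0975, 0.20/2 = 0.10 or 0.21/2 = 0.105 log. With δ = 0 and s = −0.10, the pooled fall is 0.10 log, as large as the diluted signal of a true 0.20 log effect. With δ = 0.20 and s = +0.10, it is zero. The documents give no value for s; 0.10 is an illustration. In the coated-minus-control difference s cancels.

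**4. Regression to the mean.** Suppose the highest of k cubicles is picked on pilot means. Let the between-cubicle SD be 0.3 log and let R be the share of variance in cubicle means that is real. With no coating effect, the expected fall from pilot to phase is (1 − R) × E_k × 0.3/√R, where E_k is the expected maximum of k standard normal values. For k = 6, E_k = 1.27:

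- R = 0.3: 0.7 × 1.27 × 0.3/0.548 = 0.49 log
- R = 0.5: 0.5 × 1.27 × 0.3/0.707 = 0.27 log
- R = 0.7: 0.3 × 1.27 × 0.3/0.837 = 0.14 log

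Simulation over k = 4, 6 and 10 and the same R values gives falls of 0.11 to 0.59 log from pilot to phase. From survey to phase the change is within 0.002 log of zero, because the survey is later data that played no part in the selection. The SD, k and R are all assumptions; the documents give none of them.

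**5. Can the survey serve as a baseline by position?** Study curtains were hung new at each phase start, so they have no baseline of their own. A cubicle-level survey mean B is common to both arms and cancels: (coated − B) − (control − B) = coated − control. Only a bed-position value could add precision. Sample bags carry the bed number, but plate labels carry code, area, plate number and sex of cubicle. Material Requirement lists 2,000 sponges. If that covers the whole study, 2,000 − 1,824 = 176 remain, against 76 × 8 = 608 for one full round over all curtains. For an assumed correlation r, a covariate would cut residual variance by r²: 9% at 0.3, 25% at 0.5 and 49% at 0.7. The documents give no r.

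**The case against.** The strongest reply is that this is a side analysis. The sentence speaks of evaluating a cleanliness baseline. No objective or outcome measure depends on it, and the analysis summary in Detailed Description [7] leaves it out. Efficacy rests on concurrent tests, with coated and uncoated curtains alternating in the same cubicles, so trend and cubicle selection are shared by both arms. All of that stands and limits the damage. It does not remove the problem: the test is still listed under effectiveness, at the common significance level, with no comparator. Pooling is also not stated outright. It is the natural reading of a per-ward test, and the halving depends on it.

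A reader might go further in three ways that the documents do not support.

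- **That the survey baseline itself carries regression to the mean.** Selection used the pilot, which ended on 30 October; the first survey began the next day. The expected artefact with survey data is about zero.
- **That the survey is used only in this test and a usable baseline is wasted.** The sentence does not name the survey, and the period ANOVA may use it. Nothing shows that survey samples were taken, or can be linked, by bed.
- **That calling primary outcome 1 a change promises a change from baseline.** Its definition is a percentage difference between control and treatment curtains.

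**Conclusion.** The point holds for one supporting test. An uncontrolled before-after comparison by ward cannot separate the coating from time. If curtains are pooled, it shows about 0.10 log of a true 0.195 log effect, so a common drift of that size could imitate or cancel it. This rests on equal numbers of coated and uncoated curtains, which the plan states, and on pooling, which it implies. Regression to the mean matters only if pilot data serve as before; its size depends on figures the documents do not give. The primary coated-versus-control comparison is not biased by any of this, and leaving out a baseline covariate does not bias it either. The possible gain in precision from a survey covariate cannot be known from the documents.

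**What to change.** In Data Analysis:

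1. State which data are the before values, and exclude pilot data from any baseline.
2. State that the ward before-after test is not evidence of a coating effect.
3. Report before-after changes separately for coated and control positions and interpret only their difference, with phase in the model. If the survey exists only at cubicle level, this reduces to the concurrent coated-minus-control contrast, which should then be reported instead.
4. Only if survey counts exist and can be linked by bed position, add the position's survey mean log count as a covariate in the coated-versus-control comparison.

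The study is complete, so the cost is a change of wording and a rerun of one analysis, plus a data merge if step 4 proves possible. The downside is the loss of one supporting before-after figure.
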